22.2 Definition of Expectedness

Any adverse event is considered "unexpected" if it is not listed in the investigator brochure or the package insert or is not listed at the specificity or severity that has been observed. If neither is available, then the protocol and consent are used to determine an unexpected adverse event.

22.3 Pregnancy

Pregnancy will be followed within the context of this study. Any pregnancies that occur while a participant is enrolled in the study will be captured on a pregnancy CRF and not separately reported as an AE or SAE. Pregnant women should be engaged by their site medical provider in a shared decision-making process to determine whether they remain on medication for OUD and which medication to use. The pregnancy followed until an outcome is known.

22.4 Medical and Psychiatric History

A thorough medical and psychiatric history during the screening phase should record any chronic, acute, or intermittent preexisting or current illnesses, diseases, symptoms, or laboratory signs of the participant, to avoid reporting pre-existing conditions as new events and to assist in the assessment of worsening in intensity or severity of these conditions that would indicate a TSE or SAE.

Stable chronic conditions, such as arthritis, which are present prior to clinical trial entry and do not worsen are not considered TSEs.

22.5 Site's Role in Eliciting and Reporting Safety Events

Appropriately qualified and trained personnel will elicit participant reporting of TSEs and SAEs at each study visit designated to collect these events. TSEs (medical and/or psychiatric) assessment will initiate with participant consent and follow-up of ongoing events will continue through resolution or 30 days post last study visit. Study personnel will obtain as much information as possible about the reported TSE/SAE to complete the TSE/SAE forms and will consult with the Safety Monitor/Medical Monitor as warranted.

Standard reporting, within 7 days of the site becoming aware of the event, is required for reportable TSEs. Expedited reporting (within 24 hours of their occurrence and/or site's knowledge of the event) is required for reportable SAEs (including death and life-threatening events). Sites are responsible for reporting SAEs to the IRB of record, per the IRB or record's guidelines.

Sites are required to enter reportable TSEs and SAEs in the Advantage eClinical system. The TSE form is used to capture reportable TSEs. The AE/SAE form set is used to capture SAEs (as defined in the protocol). In this protocol, only SAEs are being reported on the AE/SAE form set. Additional information may need to be gathered to evaluate SAEs and to complete the appropriate CRFs and the summary. This process may include obtaining hospital discharge reports, medical records, autopsy records or any other type records or information necessary to provide a complete and clear picture of the serious event and events preceding and following the event. If the SAE is not resolved or stable at the time of the initial report or if new information becomes available after the initial report, follow-up information must be submitted as soon as possible.

Any serious adverse reactions will be followed until resolution or stabilization for as long as possible beyond the end of the study. If the study team is unable to follow up with individuals with reportable safety events, every effort will be made to connect these individuals with the appropriate community-based treatment.

22.6 Site's Role in Assessing Severity and Causality of Adverse Events

Appropriately qualified and trained study personnel will conduct an initial assessment of seriousness, severity, and causality when eliciting participant reporting of adverse events. A study medical clinician will review reportable safety events for seriousness, severity, and causality on at least a weekly basis.

22.7 Guidelines for Assessing Severity

The severity of an adverse event refers to the intensity of the event.

Grade 1	Mild	Transient or mild discomfort (typically <48 hours), no or minimal medical intervention/therapy required, hospitalization not necessary (non-prescription or single-use prescription therapy may be employed to relieve symptoms, e.g., aspirin for simple headache, acetaminophen for post-surgical pain)
Grade 2	Moderate	Mild to moderate limitation in activity, some assistance may be needed; no or minimal intervention/therapy required, hospitalization possible but unlikely.
Grade 3	Severe	Marked limitation in activity, some assistance usually required; medical intervention/ therapy required, hospitalization possible.

22.8 Guidelines for Determining Causality

The site medical clinician will use the following question when assessing causality of an adverse event to study medication/intervention where an affirmative answer designates the event as a suspected adverse reaction:

Is there a reasonable possibility that the study medication/intervention caused the event?

22.9 Site's Role in Monitoring Safety Events

Local quality assurance monitors will review study sites and respective study data on a regular basis and will promptly advise sites to report any previously unreported safety issues and ensure that the reportable safety-related events are being followed to resolution and reported appropriately. Staff education, re-training or appropriate corrective action plan will be implemented at the participating site when unreported or unidentified reportable TSEs or serious events are discovered, to ensure future identification and timely reporting by the site.

22.10 Sponsor's Role in Safety Management Procedures of AEs/SAEs

A NIDA-assigned Safety Monitor/Medical Monitor is responsible for reviewing all serious adverse event reports. All reported SAEs will generate an e-mail notification to the Safety Monitor/Medical

Monitor, Lead Investigator, and designees. All SAEs will be reviewed by the Safety Monitor/Medical Monitor in Advantage eClinical and, if needed, additional information will be requested. The Safety Monitor/Medical Monitor will also report events to the sponsor and the DSMB as required. The DSMB will receive summary reports of all targeted safety events and SAEs annually, at a minimum. The DSMB or the NIDA assigned Safety Monitor/Medical Monitor may also request additional and updated information. Details regarding specific targeted safety events or SAEs, their treatment and resolution, will be summarized by the Safety Monitor/Medical Monitor in writing for review by the sponsor and DSMB. Subsequent review by the Safety Monitor/Medical Monitor, DSMB, FDA and ethics review committee or IRB, the sponsor, or relevant local regulatory authorities may also suspend further trial treatment at a site. The study sponsor, DSMB and FDA retain the authority to suspend additional enrollment and treatments for the entire study as applicable.

22.11 Regulatory Reporting for a non-IND study

If an SAE meets the expedited reporting criteria (serious and unexpected suspected adverse reactions), the Safety Monitor/Medical Monitor on behalf of the sponsor will provide an SAE narrative summary.

22.11.1 Reporting to the Data and Safety Monitoring Board

[figure not shown]
The DSMB will receive listing of TSEs and summary reports of all SAEs at a frequency requested by the DSMB, but at least annually. Furthermore, the DSMB will be informed of expedited reports of SAEs.

22.12 Participant Withdrawal

The site medical clinician must apply his/her clinical judgment to determine whether or not an adverse event is of sufficient severity to require that the participant be withdrawn from further study medication administration/study intervention. The site medical clinician should consult with the site.

Principal Investigator, the Lead Investigator and/or Safety Monitor/Medical Monitor as needed. If necessary, a site medical clinician may suspend any trial treatments and institute the necessary medical therapy to protect a participant from any immediate danger. A participant may also voluntarily withdraw from treatment due to what he/she perceives as an intolerable adverse event or for any other reason. If voluntary withdrawal is requested, the participant will be asked to complete an end-of-medication visit to assure safety and to document end-of-medication outcomes and will be given recommendations for medical care and/or referrals to treatment, as necessary.

22.13 Adverse Event Reporting (Chart)

23.0 APPENDIX B: DATA AND SAFETY MONITORING PLAN

1.0 BRIEF STUDY OVERVIEW

This is an open-label, multi-center, stepped-wedge cluster randomized trial. It will be conducted in 6 CTN-affiliated Community Treatment Programs (CTPs) that provide inpatient/residential detoxification services and have the capacity to provide ongoing outpatient treatment with extended-release naltrexone (XR-NTX). All sites will first implement the control procedure (Standard, 14-day procedure; SP), to establish the within-site comparison condition, and then at selected staggered time-points (steps) will switch to implementing only the experimental procedure (Rapid, 5-7-day procedure: RP). Implementation of RP at study sites will be staggered by 4 months and the order in which sites will cross-over to RP will be randomly chosen. The primary goal of the study is to determine whether the Rapid method of initiating treatment with XR-NTX is non-inferior to the standard method. Secondary objectives include comparing RP and SP for craving, withdrawal, retention, abstinence, depression and anxiety, and safety measures. Other exploratory outcomes include predictors of induction success, economic analyses, and barriers to implementation.

2.0 OVERSIGHT OF CLINICAL RESPONSIBILITIES

A. Site Principal Investigator

Each participating site's Principal Investigator (PI) is responsible for study oversight, including ensuring human research subject protection by designating appropriately qualified, trained research staff and medical clinicians to assess, report, and monitor adverse events.

All safety events (TSEs and SAEs) occurring during the course of the clinical trial will be collected, documented, and reported by the investigator or sub-investigators according to the protocol.

The occurrence of TSAEs and serious adverse events (SAEs) will be assessed at each clinic visit during the study. Serious adverse events will be followed until considered resolved or stable.

Reportable TSAEs are required to be entered into the data system within 7 days of the site staff becoming aware of the event. Reportable SAEs (including death and life-threatening events) are required to be entered into the data system within 24 hours of site's knowledge of the event.

B. CCC Safety Monitor/Medical Monitor

The NIDA CTN Clinical Coordinating Center's (CCC) Safety Monitor/Medical Monitor or designee is responsible for reviewing all targeted safety events and serious adverse events reported. The CCC Safety Monitor/Medical Monitor is alerted via email each time an SAE is reported in the EDC. All SAEs will be reviewed at the time they are reported in the EDC. The Safety Monitor/Medical Monitor or designee will also indicate concurrence or not with the details of the report provided by the site PI. Where further information is needed, the Safety Monitor/Medical Monitor or designee will discuss the event with the site staff. Reviews of SAEs by the CCC Safety Monitor/Medical Monitor or designee will be documented in the Advantage eClinical data system and will be a part of the safety database. All TSEs are reviewed on a weekly basis to observe trends or unusual events.

C. Voluntary Regulatory Reporting in non-IND Trials:

For non-IND trials, if an event meets expedited reporting criteria (serious, related and unexpected) the CCC Safety Monitor/Medical Monitor will provide an SAE narrative summary.

D. Data and Safety Monitoring Board (DSMB)

The NIDA CTN DSMB affiliated with this trial will be responsible for conducting periodic reviews of accumulating safety, trial performance, and outcome data. Reports will be generated and presented for Data and Safety Monitoring Board (DSMB) meetings. The DSMB will receive listings of targeted safety events and narratives of all SAEs at a frequency requested by the DSMB, but at least annually. Furthermore, the DSMB will be informed of expedited reports of SAEs. The DSMB will make recommendations to NIDA CCTN as to whether there is sufficient support for continuation of the trial, evidence that study procedures should be changed, or evidence that the trial (or a specific site) should be halted for reasons relating to safety of the study participants or inadequate trial performance (e.g., poor recruitment).

Following each DSMB meeting, the NIDA CCTN will communicate the outcomes of the meeting, based on DSMB recommendations, in writing to the study Lead Investigator. This communication summarizing study safety information will be submitted to participating IRBs.

E. Quality Assurance (QA) Monitoring

The monitoring of the study site(s) will be conducted on a regular basis using a combination of NIDA CCTN CCC monitors (if applicable) and the local Node QA Monitors (if applicable). Investigators will host periodic visits for the monitors. The purpose of these visits is to assess compliance with the protocol, GCP requirements, and other applicable regulatory requirements, as well as to document the integrity of the trial progress. The investigative site will provide direct access to all trial related sites (e.g., pharmacy, research office), source data/documentation, and reports for the purpose of monitoring and auditing by the monitors, as well as inspection by local and regulatory authorities. Areas of particular concern will be the review of inclusion/exclusion criteria, participant Informed Consent Forms, protocol adherence, safety monitoring, IRB reviews and approvals, regulatory documents, participant records, study drug accountability, and Principal Investigator supervision and involvement in the trial. The monitors will interact with the site staff to identify issues and re-train the site as needed to enhance research quality.

Site Visit Reports will be prepared by the NIDA CCC monitors following each site visit. These reports will be sent to the site Principal Investigator, the study Lead Investigator and NIDA CCTN.

Local Node QA site visit reports will be prepared following each site visit, as applicable. These reports are sent to those entities required of them by the Lead Investigative team, generally including the Lead Investigator, site Principal Investigator, Node PI and a CCC representative, usually the protocol specialist for the study.

F. Management of Risks to Participants Confidentiality

Confidentiality of participant records will be secured by the use of study codes for identifying participants on CRFs, and secure storage of any documents that have participant identifiers on

site, as well as secure computing procedures for entering and transferring electronic data. The documents or logs linking the study codes with the study participant on site will be kept locked/securely stored separately from the study files and the medical records. No identifying information will be disclosed in reports, publications or presentations.

3.0 Information That Meets Reporting Requirements

The consent form will specifically state the types of information that are required for reporting and that the information will be reported as required. These include suspected or known sexual or physical abuse of a child or elders, or threatened violence to self and/or others.

4.0 Participant Protection

The site's study clinician or other designated and qualified individual will evaluate all pertinent screening assessments prior to participant enrollment to ensure that the participant is eligible and safe to enter the study. Safety events and concomitant medications will be assessed and documented at each study visit. Individuals who experience a safety event that compromises safe participation in a study will be discontinued from further medication administration/intervention and provided referrals for other treatment or to specialized care. Study personnel will request that the participant complete an end-of medication visit to assure safety and to document end-of-medication outcomes.

5.0 Pregnancy

Participants who are found to be pregnant during the screening will not be enrolled in the study. Pregnant women should be engaged by their site medical provider in a shared decision-making process to determine whether they remain on medication for OUD and which medication to use. The site staff will follow the participant until an outcome of the pregnancy is known and reported.

6.0 Study Specific Risks

Risk of Overdose

Opioid detoxification carries a moderately high risk of relapse and a risk of opioid overdose if one uses a significant amount of opioids after losing tolerance. Self-administration of large doses of opiates may override the blockade produced by naltrexone resulting in an opiate overdose with its attendant risks, including respiratory depression and death. Participants will be warned of the severe danger of using opiates, including trying to override the blockade. Also, participants who have stopped naltrexone and resume opiates will not be tolerant initially, so that the quantities of opiates self-administered prior to treatment, when they were tolerant, may be quite dangerous in the non-tolerant state. Participants will be warned of this. Participants who self-administer opiates to the point of somnolence or stupor will be removed from the trial and referred to inpatient detoxification or agonist maintenance treatment. Until such individuals are accepted for treatment elsewhere, they will remain at the site where they will be offered therapy and treated in the open label manner for the duration of trial.

Risks of Naltrexone

The possible side effects of naltrexone in individuals with opioid dependence may include: a period

of more severe withdrawal symptoms due to precipitated withdrawal, difficulty sleeping, anxiety, nervousness, abdominal pain/cramps, nausea and/or vomiting, low energy, joint muscle pain, and headaches. Less common side effects include loss of appetite, diarrhea, constipation, increased thirst, increased energy, feeling down, irritability, dizziness, skin rash, delayed ejaculation and chills.

Naltrexone has been associated with reversible hepatocellular injury indicated by elevated liver enzymes when administered at doses substantially greater than the 50mg per day dose recommended for maintenance treatment of OUD and proposed for the present study. When used in the recommended dose range in opiate-dependent patients, this risk is remote (Brahen *et al.*, 1988). Naltrexone is therefore contraindicated in patients with acute hepatitis or liver failure, and such patients are excluded from the study. Patients with hepatic enzyme levels greater than 5 times the upper limit of normal are therefore excluded.

In the event of a medical emergency requiring opiate analgesia, an individual on naltrexone will require higher doses of opiates than normally administered. Participants will be informed of this and will be given a naltrexone medication card to carry in their wallet.

Naltrexone does not block intoxicating effects of other drugs such as cocaine, sedatives, or alcohol and it does not reduce the risk of using these substances.

Risks of Opioid Withdrawal

During XR-NTX induction procedure, participants are likely to experience mild to moderate severity opioid withdrawal, and it is possible that the withdrawal will be more severe in the group receiving Rapid XR-NTX induction. Opioid withdrawal may cause agitation, bone and joint aches, restlessness, runny nose and tearing, nausea, vomiting, diarrhea, anxiety or irritability, elevated pulse and blood pressure and other signs of sympathetic arousal, and sometimes confusion. Adjunctive medications will be used to alleviate the severity of withdrawal.

Risks of Ancillary Medications

Opioid withdrawal symptoms are treated with clonidine, an alpha-2-adrenergic receptor agonist which reduces sympathetic nervous system output produced by opiate withdrawal; clonazepam, a benzodiazepine which reduces the anxiety and dysphoria and permits sleep; and zolpidem or trazodone for insomnia. Clonidine may produce somnolence, dry mouth, drowsiness, dizziness, constipation, hypotension, syncope, bradycardia and QT prolongation. Clonazepam commonly may produce somnolence, poor muscle control, loss of inhibition, constipation, respiratory infection and infection. Trazodone may produce drowsiness, sedation, dizziness, constipation, and blurred vision. Zolpidem may produce drowsiness, sedation, and headache. The procedure is conducted in an inpatient setting with a medical professional present at all times, to permit close monitoring of vital signs and mental status.

Risks of XR-NTX injection

Risk of XR-NTX injection involves possible irritation at the injection site. XR-NTX injections may be followed by a period of, suicidal thoughts, pain, tenderness, induration, redness, swelling,

abscess, sterile abscess, and pruritus. Cases of serious injection site reactions, some of which involved surgical intervention, have been reported.

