10.5.7 XR-NTX Discontinuation Post-Induction

XR-NTX may be discontinued in the event of intolerable side effects or safety concerns preventing further medication treatment (e.g., pregnancy), relapse where restarting XR-NTX is not possible, or the end of the active treatment phase. Participants discontinuing medication prior to Week 8 continue within the same study assessment schedule. All participants who end treatment early (prior to Week 8) are encouraged to complete an End of Medication Treatment visit. In all cases of treatment discontinuation, the research and clinical team will make an effort to arrange for continued community treatment, as appropriate and available, including further XR-NTX and Buprenorphine-Naloxone (Suboxone®) (BUP-NX), or methadone maintenance and intensive outpatient psychosocial aftercare. For participants who do not wish to continue with XR-NTX, or for whom community resources to continue with XR-NTX are not available, the study will make alternative arrangements to make sure there is no gap in providing medication-based treatment (e.g., buprenorphine or methadone) as clinically appropriate to minimize the risk of relapse and related adverse outcomes such as an overdose.

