10.6 End of Study

Participants will have their last study visit at the end of post-induction Week 8. An effort will be made to assess all participants at Week 8 post-induction or induction failure. P55 assessments will be completed at that time.

Aggressive outreach procedures will be implemented to locate and assess all study participants to minimize missing data.

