15.2 Medications Prohibited/Allowed During Trial

Opioid agonist that are not prescribed as part of the trial (e.g., buprenorphine) will not be allowed for the duration of the trial. Though, participants will not be withdrawn if they use illicit opioids including non-prescribed buprenorphine or methadone.

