The induction phase for enrolled participants (within both RP and SP) begins with day of admission (induction phase Day 1) and ends on the day of XR-NTX receipt or day of failure of the induction protocol. The maximum length of the induction phase is 30 days. For participants who leave the unit prior to Day 30, the date of leaving the unit without a medication would be equivalent to date of failure as recorded on the EOI form per the CRF manual. Daily and weekly assessments will be conducted during the induction phase as follows:

- Daily assessments (DMA, Low Dose Naltrexone Titration [LDN] for the Rapid Protocol only, COW, OCI, SBW, Psychosocial and Medical Treatment Participation log [PST]).

- Weekly assessments (GA7, PHQ).
- Assessments collected prior to first XR-NTX injection include UDS (all participants) and PBC (females only).
- Data will be collected retrospectively starting with induction phase Day 1, using medication flowsheets and EMR abstraction (performed and confirmed by study staff). The following assessments may be retrospectively collected/abstracted: DMA, COW, UDS and PBC.
- End of Induction (EOI) and End of Induction Survey (EIP) are collected at the end of the induction phase regardless of whether the participant receives their first dose of XR-NTX on the unit, if the participant terminates the induction protocol early, or if they exceed the maximum window allowed for the induction phase.

Post-Induction Phase Assessments (Week 1 – Week 8)

The post-induction phase will begin the day after receiving XR-NTX injection or the day after failure of the induction protocol (Day 1 post-induction). During the 8-week post-induction phase, participants will receive medication management visits per the site's standard clinical practice, plus an additional two XR-NTX injections, expected at four and eight weeks after the first XR-NTX injection, along with other psychosocial treatment as per the standard of care provided by each site. The following assessments will be conducted during post-induction phase at Weeks 1, 2, 3, 4, 6 and 8: Missed Visit and Visit Documentation (V97), TAP/T97/M97, MGT, OCO, ODQ, SBW, OES, GA7, PHQ, PST. UDS (all participants) and PBC (females only) will be assessed prior to each XR-NTX injection. Additional assessments will be performed at week 3 (PSA) and week 4 and 8 (INN, NMS/NM2).

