Note that participants who fail the induction phase will still be enrolled into the post-induction phase but only assessed at Weeks 4 and 8. Participants who discontinue XR-NTX early (i.e. do not receive both injections) will complete the Early End of Medication Visit and the following assessments will be performed: V97, CMX, MGT, End of Medication (EOM), and End of Medication – Self-Reported (EO2).

Other assessments will be performed as needed: Injection Site Abnormality (INA), Mental Health Follow-Up Assessment (MHA), Study Completion (STC).

In addition to the above assessments, the study will collect data on implementation facilitation outcomes: Organization Level Clinical Implementation (OLC) at the start of each step at all sites, Pre/Post Organizational Readiness to Change Assessment (ORCA) (OR1/OR2) prior to and at the end of RP implementation step at the randomized site, Pre/Post Fidelity to Implementation Checklist (FC1/FC2) at the start and end of RP implementation step at the randomized site. OR1/OR2 collect provider/staff level data whereas OLC and FC1/FC2 collect site level data.

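### Appendix B makes removal from the trial mandatory after opiate use to somnolence or stupor, against Section 15.2, and would stop scheduled overdose assessment in a high-risk group

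*Protocol*

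**What the plan says.** Protocol Appendix B, 6.0 Study Specific Risks (Risk of Overdose): "Participants who self-administer opiates to the point of somnolence or stupor will be removed from the trial". They are referred to inpatient detoxification or agonist maintenance. Until accepted elsewhere they stay at the site and are offered therapy. Study assessments are not mentioned.

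Other parts of the protocol read differently:

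- Section 15.2: "participants will not be withdrawn if they use illicit opioids including non-prescribed buprenorphine or methadone".
- Section 10.5.7, where relapse is one reason for stopping XR-NTX: "Participants discontinuing medication prior to Week 8 continue within the same study assessment schedule".
- Section 10.6: "Aggressive outreach procedures will be implemented to locate and assess all study participants to minimize missing data".
- Appendix B, 4.0 Participant Protection, on participants whose safety event makes continued participation unsafe: they "will be discontinued from further medication administration/intervention and provided referrals for other treatment or to specialized care".
- Section 10.9: the default is to follow everyone to the end of the study. The exceptions are withdrawal of consent, death, or a decision by the investigator or sponsor to end enrollment for any reason. Relapse and non-adherence are among the possible reasons listed.

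On data collection, SAP 2.2.2 says "The following assessments will be conducted during post-induction phase at Weeks 1, 2, 3, 4, 6 and 8". The list that follows includes the Overdose Questionnaire (ODQ) and Timeline Followback (TLFB). Induction failures are assessed at Weeks 4 and 8 only. For the early end-of-medication visit, SAP 2.2.2 says "the following assessments will be performed: V97, CMX, MGT, End of Medication (EOM" and then adds only the self-reported end-of-medication form.

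**The concern.** A site whose participant uses opiates to the point of stupor cannot obey both Appendix B 6.0 and Section 15.2. If it follows Appendix B, it stops asking about overdose in someone who has just shown overdose-level use.

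This matters for one outcome in particular. SAP 8.4 lists overdoses over the eight post-induction weeks within a key secondary safety outcome. SAP 10.5 takes non-fatal overdoses from the ODQ at the post-induction visits. The Table 54 shell reports overdoses for Day 1 to 28 and for after Day 28 to Day 56 under the arm totals, with no rule for people who are no longer being asked. A later non-fatal overdose in a removed participant would be counted as no overdose unless it reached the study by another route.

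The opioid-use outcome is less exposed. SAP 8.4 covers all eight weeks, but Table 5 limits that outcome to use while on study medication.

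**Working it through.** The plan gives no figure on this point, so there is none to reproduce. The check compares the rules and then counts what a removed participant would lose.

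**1. The rules side by side**

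- Appendix B 6.0 against 15.2: a direct conflict. One orders removal after a form of opioid use. The other excludes withdrawal for illicit opioid use, whatever its severity.
- Appendix B 6.0 against 10.5.7 and 10.6: tension only. Section 10.5.7 concerns stopping medication, and 10.6 describes effort and outreach toward study participants.
- Appendix B 6.0 against Appendix B 4.0: the latter stops medication or intervention and requests an end-of-medication visit. The narrower wording was therefore available in the same appendix.
- Appendix B 6.0 against 10.9: removal is possible under both, but discretionary in 10.9 and mandatory in the appendix.

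**2. Assessments lost per removed participant**

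Inputs: visit days 6, 14, 21, 28, 42 and 56 (SAP 3.2.2); ODQ and TLFB at all six visits (SAP 2.2.2); safety window ending 30 days after the last study visit (SAP 3.2.5). It is assumed that removal directly follows the visit shown and that this visit is the last study visit.

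Formulas: assessments lost = 6 − visits attended; days lost = 56 − d; window end = d + 30; shortfall = 56 − (d + 30), or 0 if negative.

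| Last visit | Day d | ODQ and TLFB lost | Days to Day 56 | Window ends | Shortfall |
|---|---|---|---|---|---|
| Week 1 | 6 | 5 of 6 | 50 | Day 36 | 20 |
| Week 2 | 14 | 4 of 6 | 42 | Day 44 | 12 |
| Week 3 | 21 | 3 of 6 | 35 | Day 51 | 5 |
| Week 4 | 28 | 2 of 6 | 28 | Day 58 | 0 |
| Week 6 | 42 | 1 of 6 | 14 | Day 72 | 0 |

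An induction failure loses 2 of 2 assessments if removed before Week 4, and 1 of 2 if removed after it. An end-of-medication visit, if attended and counted as the last study visit, moves the window later and shrinks the shortfall.

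**3. What the remaining routes would capture**

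- The end-of-medication column of Protocol Table 7 has adverse event and serious adverse event (SAE) assessment and the Death Form, but no ODQ or TLFB.
- Overdoses that meet SAE criteria are also reported as SAEs (Protocol 12.3.4 and 12.3.13), so the triggering event may still be recorded.
- The records fallback in Protocol 12.2.5, for participants who do not complete follow-up, covers medication for opioid use disorder only.
- The safety window defines a period but schedules no questionnaire.

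What remains exposed is a later non-fatal overdose that is not reported by another route.

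**4. Outcomes not materially affected**

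The primary outcome (SAP 8.1) is settled at the end of induction on the unit. The binary retention outcome (SAP 8.5) depends on whether a further injection was given, which does not rest on the lost questionnaires.

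**The case against.** The best defense is that removal is not foreign to the main protocol. Section 10.9 lets the investigator or sponsor end enrollment for any reason and names relapse. One can also read Section 15.2 as a general rule about drug use and stupor as a specific danger that overrides it. The first point stands and narrows the issue to mandatory versus discretionary removal. The second is a possible reading, but no text states such an exception.

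It can also be said that Appendix B is carried-over text. The same section refers to a 50 mg daily naltrexone dose as proposed for this study and to an exclusion for raised liver enzymes that Section 8.2 does not contain. The appendix overview still has all sites starting on the standard procedure. This makes it less likely that the rule is used, and nothing shows that it has been. It remains in the current protocol, worded as mandatory.

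A reader might infer that overdose follow-up ends altogether. The documents do not support that: SAE and death reporting, the requested end-of-medication visit and the 30-day window all remain, and the person stays in care at the site until placed elsewhere.

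A reader might also infer that the gap would be hidden, because SAP 4.3 does not count visits after termination as missed. That goes too far. Early terminations with reasons, and Day 28 and Day 56 attendance, are tabulated by procedure, so the loss would be partly visible. The disposition shells have no category specific to this rule. The missing denominator rule in Table 54 affects every dropout, not only these.

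**Conclusion.** The point holds as an inconsistency worth correcting. Appendix B 6.0 orders removal where Section 15.2 says participants will not be withdrawn. It also runs against the retention intent of 10.5.7 and 10.6 and goes further than Appendix B 4.0. If applied, it stops scheduled ODQ and TLFB assessment, with a loss per inducted participant ranging from 5 of 6 assessments (removed after Week 1) to 1 of 6 (after Week 6).

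It is tempting to conclude that the overdose comparison between procedures is biased. The documents do not support that: they give no removal rate, overall or by arm, so neither the direction nor the size of any effect on a rate can be derived. The conclusion rests on two assumptions: that sites would apply the rule as written, and that removal ends study assessments, which the appendix implies but does not spell out.

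**What to change.** In Appendix B 6.0, replace removal from the trial with *discontinued from further study medication/intervention*, in line with Appendix B 4.0. Then add: *Scheduled assessments, at minimum the Week 4 and Week 8 TLFB and Overdose Questionnaire, continue unless consent is withdrawn.* When to stop medication and where to refer remain clinical decisions.

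A urine screen at those visits is optional. SAP 2.2.2 ties it to injections ("UDS (all participants) and PBC (females only) will be assessed prior to each XR-NTX injection"), as does the footnote to Protocol Table 7, so requiring it without an injection would mean editing both.

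The cost is a small wording amendment that needs IRB approval (Protocol 17.2), and continued visits for the participants affected, probably few. The Week 4 and Week 8 visits and forms already exist for induction failures. If enrollment has finished, the sponsor can instead check whether anyone was removed under this rule and add a footnote to Table 54.
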